6.1.1 Stopping guidelines

There are no formal statistical criteria for stopping the trial early. Decisions to stop the trial early on grounds of safety or futility will be made by the TSC.

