6.2 Harms

Adverse Events (AE) are any clinical change, disease or disorder experienced by the participant during their participation in the trial, whether or not considered related to the intervention being investigated. Adverse Events associated with participating in the study are considered unlikely. Such adverse events may include participants becoming distressed or anxious during assessment or therapy sessions, or during the in-depth interview.

Adverse events not related to the study may include:

Participants reveal to RAs or trial clinicians unrelated new medical issues which require an
assessment by a healthcare professional (e.g. fits or seizures, worsening visual difficulties,
increased frequency or severity of headaches, accidents or injuries such as falls).

Participant may score as 'distressed' on the GHQ-12 (scoring over 3) indicating low mood at any of
the assessment points; or may discuss symptoms of depression or anxiety during therapy sessions
or the in-depth interview.

Risks arising in the home or within the family.

If these adverse events do not lead to any of the outcomes listed a-g below, they will be considered non-serious. Their reporting is covered in the next section. RAs and trial clinicians will be trained on how to respond to such events (see 6.2.2 below).

Serious Adverse Events (SAEs) are considered unlikely in this project, however, they may still occur. Strokerelated events will not be reported as SAEs because these are expected within this population. An AE is considered a SAE if it results in one of the following outcomes:

- a) Death
- b) Suicide
- c) Life-threatening (i.e. with immediate, not hypothetical, risk of death at the time of the event, e.g. further stroke, cardiovascular event, serious infection)
- d) Requires in-patient hospitalisation (hospitalisation for elective treatment of a pre-existing condition is not included)
- e) Increased severe and persistent disability, where severe indicates significant deterioration in the participant's ability to carry out their activities of daily living; and persistent indicates four weeks continuous duration.
- f) Any other important medical condition, which, though not included in the above, may jeopardise the participant and may require medical or surgical intervention to prevent one of the outcomes listed.
- g) Any episode of deliberate self-harm

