6.2.1 Reporting AEs, SAEs, SARs and SUSARs

AEs (including SAEs, SARs and SUSARs) may be identified by RAs, the trial clinicians, the qualitative RA or the CI. All research staff will be responsible for reporting of AEs (including SAEs, SARs, and SUSARs) throughout the project.

All adverse events will be recorded on forms, and emailed to the CI within 24-48 hours of occurrence. The SAE form includes the potential outcomes (a-g above) to facilitate research staff choosing between the AE and SAE forms. Research staff will also receive training in completing the forms and handling AEs. The forms will be completed as thoroughly as possible with all available details of the event. In the case of incomplete information at the time of initial reporting, the research staff member will still notify the CI as quickly as possible, and provide subsequent additional information as it becomes available. A record of this notification (including date of notification) will be clearly documented to provide an audit trail.

All AEs (non-serious) will be reported to the Academic Supervisory Group on a monthly basis by the CI. These events will be reported to the TSC on an annual basis (or more frequently if requested) and will be included in the safety reporting of the completed trial.

For all SAEs (including SARs and SUSARs) the CI will notify a member of the Academic Supervisory Group within 24 hours. The relationship of the event to the treatment (SAE or SAR) and expectedness of the event (SAR or SUSAR) may be assessed and indicated on the form by the research staff member. The CI will discuss with at least two members of the Academic Supervisory Group whether the SAE is in fact a SAR or SUSAR.

The CI will also inform the research sponsor of SAEs. The Academic Supervisory Group and the sponsor will decide whether the SAE needs to be reported further to relevant regulatory bodies. If the SAE is considered by the CI and Academic Supervisory Group to be a SUSAR (i.e. related and unexpected), it will be reported to the Research Ethics Committee (REC) which approved the study, as per Health Research Authority (HRA) guidelines, using a modified version of the HRA non-CTIMP SAE report form.

Reporting timelines are as follows:

- SUSARs which are fatal or life-threatening must be reported not later than 7 days after the sponsor
 is first aware of the reaction. Any additional relevant information must be reported within a
 further 8 days.

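### Section 6.2 excludes stroke-related events from SAE reporting and then names a further stroke as an SAE, so a serious further stroke has no consistent classification or reporting route

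*Protocol*

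**What the plan says.** Section 6.2 of the protocol (Harms) contains three statements that bear on a further stroke.

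- An exclusion, with its reason: "Strokerelated events will not be reported as SAEs because these are expected within this population". Stroke-related is not defined here or elsewhere in the protocol.
- The SAE definition, which follows directly: "An AE is considered a SAE if it results in one of the following outcomes". Death is (a) and in-patient hospitalisation is (d), neither with a stroke exception. Outcome (c), life-threatening events, gives as its examples "at the time of the event, e.g. further stroke, cardiovascular event, serious infection".
- The test for non-serious events, placed after the examples of events unrelated to the study: "If these adverse events do not lead to any of the outcomes listed a-g below, they will be considered non-serious".

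Section 6.2.1 sets the reporting. Every adverse event goes on a form to the CI within 24-48 hours. On which form to use, it says: "The SAE form includes the potential outcomes (a-g above) to facilitate research staff choosing between the AE and SAE forms". For serious events: "For all SAEs (including SARs and SUSARs) the CI will notify a member of the Academic Supervisory Group within 24 hours", and the sponsor is informed as well. Non-serious events go to the Academic Supervisory Group monthly and to the TSC at least annually.

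Section 5.3.2 summarises AEs, adverse reactions, SAEs, SARs and SUSARs by treatment group, as events and as people, with a 95% confidence interval for the difference in rates. On stopping, section 6.1.1 says: "Decisions to stop the trial early on grounds of safety or futility will be made by the TSC".

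**The concern.** Every participant is a stroke survivor (section 3.2.1), so a further stroke is a foreseeable event in this trial. The exclusion sentence and the SAE definition give opposite answers for it whenever it is fatal, life-threatening or leads to admission.

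The reason given for the exclusion also sits at the wrong step. Elsewhere in 6.2 and 6.2.1, expectedness separates a SAR from a SUSAR. It plays no part in deciding whether an event is serious, which depends only on outcomes (a) to (g).

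What is at stake is the SAE pathway: prompt notice to the Academic Supervisory Group, notice to the sponsor, the SAR/SUSAR judgement, and the SAE comparison by arm. Section 7.4 says that safety information will inform the decision on a definitive trial, so the SAE table needs a single rule for what it counts.

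**Working it through.** No arithmetic decides this point. The check takes one event, a further stroke that leads to in-patient admission or is immediately life-threatening, and applies each rule in turn.

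| Step | Rule | Result for this event |
|---|---|---|
| 1 | 6.2, AE definition (no stroke exception) | It is an AE |
| 2 | 6.2, SAE definition: (d) for admission; (c) for "risk of death at the time of the event, e.g. further stroke, cardiovascular event, serious infection" | It is an SAE |
| 3 | 6.2, exclusion of stroke-related events | It is not reported as an SAE |
| 4 | 6.2, test for non-serious events | It is not non-serious, because it has an (a) to (g) outcome |
| 5 | 6.2.1, choice of form by (a) to (g) | The SAE form is indicated, against step 3 |
| 6 | 6.2.1, SAE route (24 hours, sponsor) | Closed if step 3 is followed |
| 7 | 6.2.1, route for non-serious AEs (monthly) | Not applicable, by step 4 |
| 8 | 6.2, SAR and SUSAR, both defined as kinds of SAE | Not reached if step 3 is followed |
| 9 | 5.3.2, summaries by arm | Counted among AEs; counted among SAEs only if step 2 prevails over step 3 |

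Three things follow.

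1. Steps 2 and 3 contradict each other in current, operative text, and nothing elsewhere in the protocol resolves them.
2. If step 3 is followed, the event has no stated onward route. Section 6.2.1 offers only two, and steps 6 and 7 close both. What remains is the form sent to the CI.
3. The conflict is limited to stroke-related events with an (a) to (g) outcome. A stroke-related event without one is non-serious under either sentence.

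On scale, section 3.6 plans 16 participants per arm. One participant moved into or out of the SAE count changes that arm's proportion by 1/16 = 6.25 percentage points. This shows how sensitive the table is to a single classification. It does not say how many such events to expect.

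The TSC point was checked separately. Section 6.2.1 names the TSC as recipient of non-serious AEs. For SAEs it names the Academic Supervisory Group and the sponsor, and for SUSARs also the Research Ethics Committee. It states no report of SAEs to the TSC.

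**The case against.** The best defence is that stroke-related events means consequences of the index stroke, while a new life-threatening stroke falls under (c). That may well be the intention, and it suggests a missing definition rather than a plan to leave out recurrent strokes. But the protocol does not say so, and the boundary would stay unclear even then. Section 6.2 lists seizures and falls as events that become serious on an (a) to (g) outcome, and these too could be called stroke-related.

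There are also safeguards. All forms go to the CI, staff are trained, the SAE form lists the outcomes, and 6.2 provides a second opinion where classification is in doubt. These make uncorrected inconsistency between staff less likely. They do not remove the contradiction, because those giving the second opinion would work from the same text, and someone who follows the exclusion sentence may see no doubt to raise.

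A reader might infer more than the documents support:

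- **That serious strokes disappear from safety reporting.** They do not. Section 6.2.1 records every AE on a form, and 5.3.2 tabulates AEs by arm.
- **That such an event could never be judged for relatedness.** This is too absolute. Section 5.3.2 lists adverse reactions separately from serious ones, so relatedness is contemplated outside the SAE pathway. What is lost is the SAR/SUSAR assessment.
- **That further stroke is the likeliest serious event, or would make up most SAEs.** The protocol gives no recurrence rate and no expected SAE count, and it calls SAEs unlikely.
- **That the TSC would have no sight of serious events.** Its description at the front of the protocol includes advising on the monitoring of adverse events. The missing SAE report in 6.2.1 is a real gap, but it concerns all SAEs and does not follow from the stroke sentence.

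Finally, this is a small, descriptive feasibility trial of a talking therapy. That limits the consequences, but it does not make the rule usable as written.

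**Conclusion.** The point holds as an internal contradiction in 6.2: wrong as written. If the exclusion sentence is followed, a further stroke that meets (a) to (g) misses the 24-hour and sponsor notification, the SAR/SUSAR assessment and the SAE counts by arm. If the definition is followed, it gets all of these. The event is recorded as an AE either way.

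No magnitude is claimed, because the protocol gives no event rate. The conclusion assumes only that stroke-related can be read to include a further stroke, which the undefined term allows. The lack of a stated SAE report to the TSC is a secondary and separate gap.

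**What to change.** 1. In 6.2, reconcile the exclusion sentence with the SAE definition. Define stroke-related events, and state one classification and one reporting route for them, including a further stroke with an (a) to (g) outcome.
2. Use expectedness only at the SAR/SUSAR step, as 6.2.1 already does.
3. In 5.3.2, count every event with an (a) to (g) outcome by arm, with stroke-related events on a separate line so that readers can see the totals with and without them.
4. Secondarily, name the TSC in 6.2.1 as a recipient of SAE reports, since 6.1.1 gives it the decision to stop on safety grounds.

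The cost is a few lines of protocol wording and a few more SAE forms. Nothing changes in treatment, assessments or sample size.

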6.2.1 Reporting AEs, SAEs, SARs and SUSARs

AEs (including SAEs, SARs and SUSARs) may be identified by RAs, the trial clinicians, the qualitative RA or the CI. All research staff will be responsible for reporting of AEs (including SAEs, SARs, and SUSARs) throughout the project.

All adverse events will be recorded on forms, and emailed to the CI within 24-48 hours of occurrence. The SAE form includes the potential outcomes (a-g above) to facilitate research staff choosing between the AE and SAE forms. Research staff will also receive training in completing the forms and handling AEs. The forms will be completed as thoroughly as possible with all available details of the event. In the case of incomplete information at the time of initial reporting, the research staff member will still notify the CI as quickly as possible, and provide subsequent additional information as it becomes available. A record of this notification (including date of notification) will be clearly documented to provide an audit trail.

All AEs (non-serious) will be reported to the Academic Supervisory Group on a monthly basis by the CI. These events will be reported to the TSC on an annual basis (or more frequently if requested) and will be included in the safety reporting of the completed trial.

For all SAEs (including SARs and SUSARs) the CI will notify a member of the Academic Supervisory Group within 24 hours. The relationship of the event to the treatment (SAE or SAR) and expectedness of the event (SAR or SUSAR) may be assessed and indicated on the form by the research staff member. The CI will discuss with at least two members of the Academic Supervisory Group whether the SAE is in fact a SAR or SUSAR.

The CI will also inform the research sponsor of SAEs. The Academic Supervisory Group and the sponsor will decide whether the SAE needs to be reported further to relevant regulatory bodies. If the SAE is considered by the CI and Academic Supervisory Group to be a SUSAR (i.e. related and unexpected), it will be reported to the Research Ethics Committee (REC) which approved the study, as per Health Research Authority (HRA) guidelines, using a modified version of the HRA non-CTIMP SAE report form.

Reporting timelines are as follows:

- SUSARs which are fatal or life-threatening must be reported not later than 7 days after the sponsor
 is first aware of the reaction. Any additional relevant information must be reported within a
 further 8 days.
- SUSARs that are not fatal or life-threatening must be reported within 15 days of the sponsor first becoming aware of the reaction.

6.2.2 Follow-up after adverse events

It is likely that a high proportion of participants will score as 'distressed' on the GHQ-12 (i.e. score over 3), at any of the assessment time points. In a comparable population, 45% of participants six months post stroke were classified as 'distressed'⁵⁴ on the GHQ-12. RAs administering the GHQ-12 will follow a set protocol in this situation. They will firstly seek permission of the participant for the CI to contact the GP, in order to share this result. They will also advise the participant to visit their GP to consider different therapeutic options for low mood, and will offer to facilitate this (e.g. make initial phone call if requested). The participant will then be given the choice as to whether to remain in the project.

Where an RA, trial clinician, qualitative RA or CI has serious concerns about a participant's mental or physical well-being, they will be trained to respond appropriately. As above, they will encourage the participant to contact their GP, and will additionally explain to the participant that they are concerned for their well-being and will need to discuss it with the CI. They will notify the CI immediately, who will then

discuss appropriate and timely action with at least one member of the Academic Supervisory Group with a view to contacting the participant's GP and any other relevant authorities to state the concerns.

After an SAE, SAR or SUSAR, a decision will be made by the CI, in consultation with the Academic Supervisory Group and other relevant authorities, as to whether the participant should be withdrawn from either their randomised treatment allocation, or from the trial. The CI will make arrangements for further assessment and management as agreed with the relevant authorities (e.g. participant's GP), and participant.

6.3 Auditing

Several mechanisms are in place to monitor and audit trial conduct. The CI will meet with the Academic Supervisory Group at least once a month. At these meetings it is the responsibility of the CI and academic supervisors to discuss trial progress and highlight any issues requiring further input. The TSC will meet three times over the course of the project to oversee the study conduct and management.

7. Ethics and dissemination

7.1 Research ethics approval

The trial will be conducted in compliance with the principles of the Declaration of Helsinki (1996), the principles of Good Clinical Practice and in accordance with all applicable regulatory requirements including but not limited to the Research Governance Framework and the Mental Capacity Act 2005. This protocol and related documents will be submitted for review to the Health Research Authority (HRA) through the Integrated Research Application System. The study has been adopted by the North Thames Clinical Research Network. The CI will submit a final report at conclusion of the trial to the HRA, the Sponsor and Funder.

7.2 Protocol amendments

Any significant amendments to the protocol will be communicated with all relevant parties including the Academic Supervisory Group, the TSC, the sponsor, the funder, HRA and any trial registries that the study is registered with.

7.3 Informed consent

Written informed consent will be obtained from all participants who are able to give it. For participants who are physically unable to sign the form (e.g. due to weakness in dominant hand due to stroke) then

Page 37

consent will be given using a mark or line in the presence of an independent witness (who has no involvement in the trial) who will then corroborate by signing the consent form.

All our information sheets and consent forms are in line with HRA guidelines. Furthermore, we have developed participant information materials and consent forms that are accessible to people with aphasia. These materials were developed following standard aphasia-friendly principles, such as presenting one idea at a time, using short simple sentences, use of large font and white space, emboldening key words and presenting key ideas with a suitable pictorial image. We based the information sheets and consent forms on templates created by the NIHR CRN for enabling people with aphasia to participate in research (https://www.crn.nihr.ac.uk/stroke/pcpie/enabling-people-with-aphasia-to-participate-in-research-resources-for-stroke-researchers/), which has been specifically designed to facilitate the consent process with people who have aphasia. Additionally, the Aphasia Advisory Group, comprising four people with aphasia and a carer, reviewed and advised on the forms. They were highly supportive of the use of pictures and the presentation of the material. They also made a number of suggestions, which we have incorporated (e.g. how we present the group allocation process). Finally, an earlier version of the Participant Information Sheet was used in the pilot project with people with severe aphasia: their feedback also resulted in further changes (e.g. to consenting to being video recorded).

To facilitate the consent process, each participant will receive the Participant Information Sheet at least 24 hours in advance of meeting with the CI. This will mean they have a chance to discuss the project with friends or family. On the advice of the Aphasia Advisory Group, we will also make a simple video, where the CI explains about the project, and reads out the Participant Information Sheet. Where appropriate (i.e. for those potential participants with an email address; for participants who prefer spoken to written word communication), we will send this via email in advance of meeting up.

For all participants, the CI will meet them for an initial visit to discuss the research study in a location of their choice: we anticipate this will usually be their own home, although some may prefer to meet in the Roberta Williams Speech and Language Therapy Centre, at City, University of London. The CI has extensive experience at facilitating the expression and understanding of people with aphasia, and will use 'total communication' techniques (i.e. all communication modalities, such as writing, gesture, drawing, objects in the environment), as well as modify her own language so that it is more accessible to someone with aphasia. It will be a priority that the information-giving session is a two-way conversation, with the person with aphasia facilitated to take an active role, for example, in asking questions and seeking clarifications. They will be reassured that participating in the study is entirely voluntary, that choosing not to take part will not affect their normal care, and that they can change their mind at any time. It was also the advice of the Aphasia Advisory Group that the potential participant should be listened to holistically and given the

space to consider how the project might fit in with the rest of their lives. As such, we anticipate this initial session is likely to take around an hour.

Only those with capacity are eligible to take part in this project. We consider that those who lack capacity are unlikely to benefit from this particular therapy approach, as it requires actively participating in therapeutic communication, and retaining information between sessions. The Mental Capacity Act (2005) states that there should be an assumption that a person has capacity to make their own decision, unless they are unable to [1] understand the information relevant to the decision; [2] retain that information; [3] use or weigh that information; or [4] communicate their decision. As explained above, we will do all we can to ensure that the person's aphasia does not mask their competence, by facilitating both their comprehension and expression. Once the potential participant has been given the information, and had sufficient time to ask questions and discuss the project, we will make an assessment of a person's capacity to give fully informed consent. We will check that they can remember what the study is about, and can understand the information. We will do this both informally, and also by asking all potential participants three simple yes/no or forced alternative questions after information giving, to confirm they have understood key aspects of the study. These questions will be: Will the researchers visit you once or several times? Can you stop if you wish, yes or no? Is this study about a new drug OR involve talking to a Speech and Language Therapist? If potential participants cannot answer these questions correctly, it will suggest that they are unable to give fully informed consent. These participants will be thanked for their time, but it will be explained to them and their families that they are not eligible for the study, as they are unlikely to benefit from this particular intervention. They will be given information about support options available to them (e.g. local stroke groups) as appropriate.

For those that have capacity, after discussing the PIS, some individuals may wish to give their consent at this point. However, we recognise that others may prefer to have additional time in order to weigh up their options. In this case, we will organise to revisit them at a mutually convenient time. Similarly, potential participants identified by their direct care team will be given as much time as they need before deciding whether to consent to their details being passed on to the research team. It was also the view of the Aphasia Advisory Group that potential participants should have the option of expressing an interest, while stating a preference for the research team to contact them in 3 months rather than immediately.

Written informed consent to participate in in-depth interviews will also be obtained from the trial clinicians and Local Collaborators.

